5.3.5.2 Diagnosis versus Signs and Symptoms

For adverse events other than systemic reactions during or after study drug infusion (see Section 5.3.5.1), a diagnosis (if known) should be recorded on the Adverse Event eCRF rather than individual signs and symptoms (e.g., record only liver failure or hepatitis rather than jaundice, asterixis, and elevated transaminases). However, if a constellation of signs and/or symptoms cannot be medically characterized as a single diagnosis or syndrome at the time of reporting, each individual event should be recorded on the Adverse Event eCRF. If a diagnosis is subsequently established, all previously reported adverse events based on signs and symptoms should be nullified and replaced by one adverse event report based on the single diagnosis, with a starting date that corresponds to the starting date of the first symptom of the eventual diagnosis.

5.3.5.3 Adverse Events That Are Secondary to Other Events

In general, adverse events that are secondary to other events (e.g., cascade events or clinical sequelae) should be identified by their primary cause, with the exception of severe or serious secondary events. A medically significant secondary adverse event that is separated in time from the initiating event should be recorded as an independent event on the Adverse Event eCRF. For example:

- If vomiting results in mild dehydration with no additional treatment in a healthy adult, only vomiting should be reported on the eCRF.
- If vomiting results in severe dehydration, both events should be reported separately on the eCRF.
- If a severe gastrointestinal hemorrhage leads to renal failure, both events should be reported separately on the eCRF.
- If dizziness leads to a fall and consequent fracture, all three events should be reported separately on the eCRF.
- If neutropenia is accompanied by an infection, both events should be reported separately on the eCRF.

All adverse events should be recorded separately on the Adverse Event eCRF if it is unclear as to whether the events are associated.

5.3.5.4 Persistent or Recurrent Adverse Events

A persistent adverse event is one that extends continuously, without resolution, between patient evaluation timepoints. Such events should only be recorded once on the Adverse Event eCRF. The initial severity (intensity or grade) of the event will be recorded at the time the event is first reported. If a persistent adverse event becomes more severe, the most extreme severity should also be recorded on the Adverse Event eCRF. Details regarding any increases or decreases in severity will be captured on the Adverse Event Intensity or Grade Changes eCRF. If the event becomes serious, it should be reported to the Sponsor immediately (i.e., no more than 24 hours after learning that the event became serious; see Section 5.4.2 for reporting instructions). The Adverse Event eCRF should be updated by changing the event from "non-serious" to "serious," providing the date that the event became serious, and completing all data fields related to serious adverse events.

A recurrent adverse event is one that resolves between patient evaluation timepoints and subsequently recurs. Each recurrence of an adverse event should be recorded as a separate event on the Adverse Event eCRF.

5.3.5.5 Abnormal Laboratory Values

Not every laboratory abnormality qualifies as an adverse event. A laboratory test result must be reported as an adverse event if it meets any of the following criteria:

- Is accompanied by clinical symptoms
- Results in a change in study treatment (e.g., dosage modification, treatment interruption, or treatment discontinuation)
- Results in a medical intervention (e.g., potassium supplementation for hypokalemia) or a change in concomitant therapy
- Is clinically significant in the investigator's judgment

Note: For oncology trials, certain abnormal values may not qualify as adverse events.

It is the investigator's responsibility to review all laboratory findings. Medical and scientific judgment should be exercised in deciding whether an isolated laboratory abnormality should be classified as an adverse event.

If a clinically significant laboratory abnormality is a sign of a disease or syndrome (e.g., ALP and bilirubin 5×ULN associated with cholestasis), only the diagnosis (i.e., cholestasis) should be recorded on the Adverse Event eCRF.

If a clinically significant laboratory abnormality is not a sign of a disease or syndrome, the abnormality itself should be recorded on the Adverse Event eCRF, along with a

descriptor indicating whether the test result is above or below the normal range (e.g., "elevated potassium," as opposed to "abnormal potassium"). If the laboratory abnormality can be characterized by a precise clinical term per standard definitions, the clinical term should be recorded as the adverse event. For example, an elevated serum potassium level of 7.0 mEq/L should be recorded as "hyperkalemia."

Observations of the same clinically significant laboratory abnormality from visit to visit should only be recorded once on the Adverse Event eCRF (see Section [5.3.5.4](#) for details on recording persistent adverse events).

5.3.5.6 Abnormal Vital Sign Values

Not every vital sign abnormality qualifies as an adverse event. A vital sign result must be reported as an adverse event if it meets any of the following criteria:

- Is accompanied by clinical symptoms
- Results in a change in study treatment (e.g., dosage modification, treatment interruption, or treatment discontinuation)
- Results in a medical intervention or a change in concomitant therapy
- Is clinically significant in the investigator's judgment
- It is the investigator's responsibility to review all vital sign findings. Medical and scientific judgment should be exercised in deciding whether an isolated vital sign abnormality should be classified as an adverse event.

If a clinically significant vital sign abnormality is a sign of a disease or syndrome (e.g., high blood pressure), only the diagnosis (i.e., hypertension) should be recorded on the Adverse Event eCRF.

Observations of the same clinically significant vital sign abnormality from visit to visit should only be recorded once on the Adverse Event eCRF (see Section [5.3.5.4](#) for details on recording persistent adverse events).

5.3.5.7 Abnormal Liver Function Tests

The finding of an elevated ALT or AST ($>3 \times$ baseline value) in combination with either an elevated total bilirubin ($>2 \times$ ULN) or clinical jaundice in the absence of cholestasis or other causes of hyperbilirubinemia is considered to be an indicator of severe liver injury (as defined by Hy's Law). Therefore, investigators must report as an adverse event the occurrence of either of the following:

- Treatment-emergent ALT or AST $>3 \times$ baseline value in combination with total bilirubin $>2 \times$ ULN (of which $\geq 35\%$ is direct bilirubin)
- Treatment-emergent ALT or AST $>3 \times$ baseline value in combination with clinical jaundice

The most appropriate diagnosis or (if a diagnosis cannot be established) the abnormal laboratory values should be recorded on the Adverse Event eCRF (see Section [5.3.5.2](#))

and reported to the Sponsor immediately (i.e., no more than 24 hours after learning of the event), either as a serious adverse event or an adverse event of special interest (see Section 5.4.2).

5.3.5.8 Deaths

All deaths that occur during the protocol-specified adverse event reporting period (see Section 5.3.1), regardless of relationship to study drug, must be recorded on the Adverse Event eCRF and immediately reported to the Sponsor (see Section 5.4.2). This includes death attributed to progression of melanoma.

Death should be considered an outcome and not a distinct event. The event or condition that caused or contributed to the fatal outcome should be recorded as the single medical concept on the Adverse Event eCRF. Generally, only one such event should be reported. If the cause of death is unknown and cannot be ascertained at the time of reporting, "unexplained death" should be recorded on the Adverse Event eCRF. If the cause of death later becomes available (e.g., after autopsy), "unexplained death" should be replaced by the established cause of death. The term "sudden death" should not be used unless combined with the presumed cause of death (e.g., "sudden cardiac death").

If the death is attributed to progression of malignancy, "malignant neoplasm progression" should be recorded on the Adverse Event eCRF. The term "disease progression" should be avoided since it is not clearly linked to a patient's underlying malignancy.

Deaths that occur after the adverse event reporting period should be reported as described in Section 5.6.

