5.3.1 Adverse Event Reporting Period

Investigators will seek information on adverse events at each patient contact. All adverse events, whether reported by the patient or noted by study personnel, will be recorded in the patient's medical record and on the Adverse Event eCRF.

After informed consent has been obtained but prior to initiation of study drug, only serious adverse events caused by a protocol-mandated intervention (e.g., invasive procedures such as biopsies, discontinuation of medications) should be reported (see Section 5.4.2 for instructions for reporting serious adverse events).

After initiation of study drug, all adverse events will be reported until 90 days after the final dose of study drug or until initiation of another anti-cancer therapy, whichever occurs first. After this period, the investigator is not required to actively monitor patients for new events, but should report any serious adverse events that are believed to be related to treatment with RO7198457 and/or pembrolizumab in this study (see Section 5.6). Deaths should be reported as described in Section 5.3.5.8.

Ongoing adverse events thought to be related to study treatment will be followed until the event has resolved to baseline grade, the event is assessed by the investigator as stable, new anti-cancer treatment is initiated, the patient is lost to follow-up, the patient withdraws consent, or it has been determined that study treatment or participation is not the cause of the adverse event.

Instructions for reporting adverse events that occur after the adverse event reporting period are provided in Section [5.6](#).

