5.3.3 Assessment of Severity of Adverse Events

The adverse event severity grading scale for the NCI CTCAE v5.0 will be used for assessing adverse event severity unless otherwise specified. [Table 4](#) will be used for assessing severity for adverse events that are not specifically listed in the NCI CTCAE.

Table 9 Adverse Event Severity Grading Scale for Events Not Specifically Listed in NCI CTCAE

Grade	Severity
1	Mild; asymptomatic or mild symptoms; clinical or diagnostic observations only; or intervention not indicated
2	Moderate; minimal, local, or non-invasive intervention indicated; or limiting age-appropriate instrumental activities of daily living ^a
3	Severe or medically significant, but not immediately life-threatening; hospitalization or prolongation of hospitalization indicated; disabling; or limiting self-care activities of daily living ^{b, c}
4	Life-threatening consequences or urgent intervention indicated ^d
5	Death related to adverse event ^d

NCI CTCAE = National Cancer Institute Common Terminology Criteria for Adverse Events.

Note: Based on the most recent version of NCI CTCAE (v5.0), which can be found at:

http://ctep.cancer.gov/protocolDevelopment/electronic_applications/ctc.htm

- ^a Instrumental activities of daily living refer to preparing meals, shopping for groceries or clothes, using the telephone, managing money, etc.
- ^b Examples of self-care activities of daily living include bathing, dressing and undressing, feeding oneself, using the toilet, and taking medications, as performed by patients who are not bedridden.
- ^c If an event is assessed as a "significant medical event," it must be reported as a serious adverse event (see Section 5.4.2 for reporting instructions), per the definition of serious adverse event in Section 5.2.2.
- ^d Grade 4 and 5 events must be reported as serious adverse events (see Section 5.4.2 for reporting instructions), per the definition of serious adverse event in Section 5.2.2.

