5.3.5.10 Lack of Efficacy or Worsening of Incurable, Advanced Malignancy

Events that are clearly consistent with the expected pattern of progression of the underlying disease should not be recorded as adverse events. These data will be captured as efficacy assessment data only. In most cases, the expected pattern of progression will be based on RECIST criteria. In rare cases, the determination of clinical progression will be based on symptomatic deterioration. However, every effort should be made to document progression through use of objective criteria. If there is any uncertainty as to whether an event is due to disease progression, it should be reported as an adverse event.

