5.3.5.11 Hospitalization or Prolonged Hospitalization

Any adverse event that results in hospitalization (i.e., inpatient admission to a hospital) or prolonged hospitalization should be documented and reported as a serious adverse event (per the definition of serious adverse event in Section 5.2.2), except as outlined below.

An event that leads to hospitalization under the following circumstances should not be reported as an adverse event or a serious adverse event:

- Hospitalization for respite care
- Hospitalization solely for coordination of care, including hospice arrangements
- Planned hospitalization required by the protocol (e.g., for study drug administration, protocol mandated observation window, insertion of access device for study drug administration, etc.)
- Hospitalization for a preexisting condition, provided that all of the following criteria are met:

The hospitalization was planned prior to the study or was scheduled during the study when elective surgery became necessary because of the expected normal progression of the disease.

The patient has not experienced an adverse event.

- Hospitalization due solely to progression of the underlying cancer
- Hospitalization that was necessary because of patient requirement for outpatient care outside of normal outpatient clinic operating hours

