6.5 SAFETY ANALYSES

Safety analyses will be conducted in all randomized patients who received at least one dose of RO7198457 and/or pembrolizumab. Safety analyses will be performed by treatment arm and will be based on actual treatment received. Specifically, a patient will be included in the RO7198457 plus pembrolizumab arm in the safety analyses if the patient receives any amount of RO7198457, regardless of the initial treatment assignment at randomization.

Safety endpoints will include incidence and severity of adverse events (using NCI CTCAE v5.0), including serious adverse events and adverse events of special

interest, changes from baseline in clinically relevant vital signs, physical findings, and clinical laboratory results following the administration of RO7198457 plus pembrolizumab or solely pembrolizumab. Drug exposure will be summarized, including duration, dosage, and dose intensity. Verbatim description of adverse events will be mapped to the MedDRA thesaurus terms and graded according to the NCI CTCAE v5.0.

All adverse events that occur during or after the first study treatment, until 90 days after the final dose of study drug or initiation of another systemic anti-cancer therapy, whichever occurs first, will be summarized by treatment arm and NCI CTCAE grade. In addition, serious adverse events and adverse events leading to study treatment discontinuation or interruption will be summarized accordingly. Multiple occurrence of the same event will be counted once at the maximum severity. Laboratory data with values outside of the normal ranges will be identified. Additionally, selected laboratory data will be summarized by treatment arm and grade. Vital signs will also be summarized by treatment arm and visit. Deaths and causes of deaths will be summarized. Analyses of safety endpoints will be conducted at the time of the primary efficacy analysis.

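### Grade 5 and, to a lesser degree, serious adverse event totals will mix deaths from melanoma progression with toxicity, because Section 6.5 does not separate the progression term

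*Combined protocol and SAP*

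**What the plan says.** - **Fatal progression is recorded.** Section 5.3.5.8 requires all deaths in the reporting period, whatever their relation to study drug, on the Adverse Event eCRF, with immediate reporting. It adds: "This includes death attributed to progression of melanoma". The prescribed term is *malignant neoplasm progression*.
- **Other progression is not.** Section 5.3.5.10: "Events that are clearly consistent with the expected pattern of progression of the underlying disease should not be recorded as adverse events". It continues: "These data will be captured as efficacy assessment data only". No exception for fatal cases is stated, and Sections 5.3.5.8 and 5.3.5.10 do not refer to each other. Section 5.3.5.11 lists among the hospitalisations that are neither adverse nor serious events: "Hospitalization due solely to progression of the underlying cancer".
- **Fatal means serious.** Section 5.2.2 makes a fatal event serious, and a footnote to the grading table in Section 5.3.3 says: "Grade 4 and 5 events must be reported as serious adverse events".
- **The window.** Under Section 5.3.1, "adverse events will be reported until 90 days after the final dose of study drug or until initiation of another anti-cancer therapy", whichever comes first. Section 5.6 sends later deaths to the survival follow-up form.
- **The analysis.** Section 6.5 takes "All adverse events that occur during or after the first study treatment, until 90 days after the final dose of study drug" (or new systemic anti-cancer therapy) and summarises them by arm and CTCAE grade, with serious events handled in the same way. It also plans a summary of deaths and their causes. Arms are as treated: any RO7198457 places a patient in the combination arm, whatever the randomised assignment.

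**The concern.** The same disease process is left out of the safety tables while the patient lives and enters as a Grade 5 serious event if the patient dies inside the window. Incidence and severity of adverse events is the first safety endpoint (synopsis and Section 2.2). The Grade 5 row is where a reader looks for fatal toxicity of adding RO7198457. If that row also carries melanoma deaths, a difference between arms can come from disease control, or from how patients are allocated to arms in the safety analysis, and be read as a difference in toxicity. A small number of toxic deaths would also be diluted in the total.

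**Working it through.** The plan states no Grade 5, serious event or progression-death rate, so there is no figure to reproduce. The check has four steps.

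**1. Trace the rules.**

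| Event inside the window | Adverse Event eCRF? | In the Section 6.5 grade and serious event tables? |
|---|---|---|
| Non-fatal progression | No (5.3.5.10) | No |
| Hospitalisation solely for progression | No (5.3.5.11) | No |
| Death from progression | Yes (5.3.5.8) | Yes, as Grade 5 and serious |
| Any other fatal event | Yes | Yes, as Grade 5 and serious |

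The last two rows share a total. Placing the third row in Grade 5 is an inference from the fatal outcome, Section 5.2.2 and the Section 5.3.3 table; no sentence exempts it.

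**2. How much of each total could be progression?** All rates here are assumptions: progression death in the window p = 5% to 20%, other fatal events t = 1% to 3%, non-fatal serious events s = 20% to 40%, risks independent.

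- Grade 5 = 1 − (1 − p)(1 − t). Serious = 1 − (1 − Grade 5)(1 − s).
- Progression share of Grade 5, approximately p/(p + t): from 0.05/0.08 = 62.5% to 0.20/0.21 = 95%.
- Patients whose only serious event is a progression death, p(1 − t)(1 − s)/Serious: from 0.05 × 0.97 × 0.6/0.447 = 6.5% to 0.20 × 0.99 × 0.8/0.366 = 43%.

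Now give Arm B a hazard ratio of 0.6 for progression death and identical toxicity. At p = 10%, t = 1%:

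- Arm A Grade 5: 1 − 0.90 × 0.99 = 10.9%.
- Arm B: p = 1 − 0.90^0.6 = 6.1%, so Grade 5 = 7.1%.
- Serious events at s = 40%: 46.5% against 44.2%.
- With the term removed, Grade 5 is 1% in each arm.

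**3. A cross-check from a survival figure in the protocol.** Section 1.1 cites 74% one-year survival on pembrolizumab. Assume that 30% to 60% of first-year deaths fall inside the window and, generously, that all are melanoma deaths.

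- Arm A: (1 − 0.74) × 0.3 = 7.8%; × 0.6 = 15.6%; about 3 to 6 of 40.
- Arm B at a survival hazard ratio of 0.8: (1 − 0.74^0.8) = 21.4%, giving 6.4% and 12.8%. At 0.7: 19.0%, giving 5.7% and 11.4%.
- The gap runs from 7.8 − 6.4 = 1.4 to 15.6 − 11.4 = 4.2 percentage points.
- Standard error of such a difference with 40 and 80 patients: √(0.078 × 0.922/40 + 0.064 × 0.936/80) = 5.0 points, up to √(0.156 × 0.844/40 + 0.114 × 0.886/80) = 6.7 points.

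**4. Direction.** Steps 2 and 3 keep patients in their randomised arms. Section 6.5 does not, and Section 4.1.3.1 requires confirmed progression before crossover. If 25% to 50% of Arm A crossed over (assumed), the safety arms would be 30 against 90, or 20 against 100. Suppose 25% cross over, no treatment effect of any kind, and 10% in-window progression death in each randomised arm (4 of 40 and 8 of 80). If k of the four Arm A deaths follow crossover:

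- k = 0: 4/30 = 13.3% against 8/90 = 8.9%.
- k = 1: 3/30 = 10.0% against 9/90 = 10.0%.
- k = 2: 2/30 = 6.7% against 10/90 = 11.1%.

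The sign changes with k alone.

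**The case against.** Recording every death is a sound safeguard: it prevents a toxic death misread as progression from going unreported. Section 5.3.5.8 can be read as a specific rule beside the general one in 5.3.5.10, which itself sends uncertain cases to the adverse event form. The progression deaths carry one dedicated term, causality is assessed for each drug (Section 5.3.4), and Section 6.5 summarises causes of death. A reader can therefore go a good way towards separating them. The gap in step 3 is also smaller than its standard error.

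Most of this stands, and it rules out several stronger readings that a reader might infer:

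- *Grade 5 and serious event rates measure efficacy rather than toxicity.* They mix the two. All other fatal events stay in Grade 5, and only fatal progression inside the window reaches the serious event totals.
- *Fatal toxicity is hidden.* It is diluted in the totals, not concealed, given the dedicated term, the causality data and the cause-of-death summary.
- *The arm with better disease control will show fewer Grade 5 events.* The as-treated rule and crossover leave the direction open.
- *The Internal Monitoring Committee will be misled.* Its charter is not in the documents, and Section 3.1.5 does not limit what it may see.

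What the objection does not reach is the tables themselves. Section 6.5 never says that the term will be separated in the grade and serious event summaries. The deaths summary is not stated to be limited to the adverse event window, so its counts need not reconcile with the Grade 5 row.

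**Conclusion.** The point holds as one of presentation in the safety analysis. As written, the rules give Grade 5 totals, and to a lesser degree serious event totals, that combine fatal progression with toxicity, so an arm difference in them could arise with no difference in toxicity. The direction cannot be stated in advance. The sizes above are illustrative only: the share of deaths inside the window, the other event rates, the survival effect and the crossover fraction are all assumptions. Under them, most Grade 5 events would be progression deaths, while the effect on overall serious event rates is a few percentage points or less in the worked example. The primary PFS analysis is not affected. This is a cheap improvement worth making before the safety tables are produced.

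**What to change.** Keep the reporting route in Section 5.3.5.8 unchanged. In Section 6.5, state that the adverse-event-by-grade, Grade 5 and serious adverse event summaries will be shown side by side with and without *malignant neoplasm progression*, neither version replacing the other. Cross-reference 5.3.5.8 and 5.3.5.10, so that the recording of fatal progression is visibly an intended exception.

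The cost is a few sentences and a few repeated tables from data already collected. The version without the term depends on the investigator's attribution of death in an open-label trial, and a toxic death attributed to progression would drop out of it. That is the reason for keeping both versions.
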